#### 8 STRENGTH AND LIMITATION OF THE RESEACRCH METHODS

#### Strengths

The strength of this study includes use of patients' medical records for data collection, which allows data to be captured on a large, diverse cohort of patients with different characteristics in a quick and efficient manner.

Another strength is the eligibility criteria, which has been selected to be as broad as possible for the target patient population, so as to reflect the real-world clinical setting to the extent possible, and to minimize selection bias.

#### Limitations and Bias

As this is a retrospective observational study and participant enrolment in the study will be done in a consecutive manner. This approach is associated with low possibility of bias and representativeness of the enrolled sample could be affected, if there is pattern observed among a particular age group or due to any season etc. In case such selection bias is observed, then additional stratification/ subgroup can be reported in the analysis, as required.

Since this study will involve collection of existing data from medical records, misclassification bias due to recording errors is possible. Medical records may not always be complete, the availability and quality/completeness of data may vary

> PFIZER CONFIDENTIAL CT24-WI-GL03-RF03 2.0 Non-Interventional Statistical Analysis Plan 01-Jun-2020 Page 23 of 42

considerably between different sites within KSA, and there may be abstraction errors and differences in reporting standards between the different sites.

Another limitation to be considered is the characteristics of the patient population to be included in the final analysis, which may potentially be biased based on the KSA national recommendations put in place for the management and treatment of COVID-19 during the observational period. This may affect the generalizability of findings from this study across different countries in the real-world setting.

At the patient-level, misclassification of drug exposure has to be considered. Medical records provide detailed information on patient demographics, clinical characteristics, and prescribed nirmatrelvir, ritonavir treatment, but may not contain information on the intended duration of use (days of supply) and may not contain accurate information on the actual treatment pattern of nirmatrelvir, ritonavir medications by the patient ie, patient adherence (if any).

COVID-19 outcomes are dependent on individuals seeking healthcare i.e., individual may have symptoms for long but if there is not an interaction with the health system, it will be unknown.

Number	Description					
Table shells for P	Table shells for Primary objectives					
Table shell 1	Summary of patient enrolment at Index date.					
Table shell 2	Summary of demographic characteristics of patients at Index date.					
Table shell 3	Summary of clinical characteristics of patients at Index date.					
Table shell 4	Summary of COVID-19 vaccination history of patients at Index date.					
Table shell 5	Summary of previous COVID-19 infection of patients at Index date.					
Table shell 6	Summary of COVID-19 Positive infection of patients at Index date.					
Table shell 7	Summary of Nirmatrelvir/Ritonavir prescription at Index date.					
Table shell 7.1	Summary of Nirmatrelvir/Ritonavir prescription at index date by age groups.					
Table shell 7.2	Summary of Nirmatrelvir/Ritonavir prescription at index date by gender.					
Table shell 7.3	Summary of Nirmatrelvir/Ritonavir prescription at index date by BMI categories.					
Table shell 7.4	Summary of Nirmatrelvir/Ritonavir prescription at index date by smoking status.					
Table shell 7.5	Summary of Nirmatrelvir/Ritonavir prescription at index date by previous COVID-19 infection.					
Table shell 7.6	Summary of Nirmatrelvir/Ritonavir prescription at index date by COVID-19 vaccination history.					
Table shell 8	Summary of Healthcare Resource use at Index date.					

#### 9 LIST OF TABLES AND TABLE SHELLS

PFIZER CONFIDENTIAL

CT24-WI-GL03-RF03 2.0 Non-Interventional Statistical Analysis Plan 01-Jun-2020

Page 24 of 42

Table shell 8.1	Summary of Healthcare Resource use at Index date by age groups.
Table shell 8.2	Summary of Healthcare Resource use at index date by gender.
Table shell 8.3	Summary of Healthcare Resource use at index date by BMI categories.
Table shell 8.4	Summary of Healthcare Resource use at index date by smoking status.
Table shell 8.5	Summary of Healthcare Resource use at index date by previous COVID-19
	infection.
Table shell 8.6	Summary of Healthcare Resource use at index date period by COVID-19
	vaccination history.

#### Table shells for Secondary objectives

Table shell 9Summary of Healthcare Resource use during the 30 days post index date
period.

#### Table shells for stratification analysis – Secondary objectives (HCRU)

Table shell 10	Summary of Healthcare Resource use during the 30 days post index date period by age groups.
Table shell 11	Summary of Healthcare Resource use during the 30 days post index date
Table shell 12	period by gender. Summary of Healthcare Resource use during the 30 days post index date period by BMI categories.
Table shell 13	Summary of Healthcare Resource use during the 30 days post index date period by smoking status.
Table shell 14	Summary of Healthcare Resource use during the 30 days post index date period by most common medication use to treat COVID-19 in addition to nirmatrelvir, ritonavir.
Table shell 15	Summary of Healthcare Resource use during the 30 days post index date period by previous COVID-19 infection.
Table shell 15.1	Summary of Healthcare Resource use during the 30 days post index date period by number of previous COVID-19 infection.
Table shell 16	Summary of Healthcare Resource use during the 30 days post index date period by COVID-19 vaccination history.
Table shell 17	Summary of Healthcare Resource use during the 30 days post index date period by days from COVID-19 diagnosis to nirmatrelvir, ritonavir prescription.
Table shell 18	Summary of Healthcare Resource use during the 30 days post index date period by days from prescription to dispensing (if available).
Table shell 19	Summary of Healthcare Resource use during the 30 days post index date period by days from COVID 19 symptoms onset to dispensing (if available).
Table shell 20	Summary of Healthcare Resource use during the 30 days post index date period by days from COVID 19 symptoms onset to nirmatrelvir, ritonavir prescription (if available).
Table shell 21	Summary of COVID-19 PCR and /antigen test result(s) during the 30 days post index date period. (If available)

#### PFIZER CONFIDENTIAL

CT24-WI-GL03-RF03 2.0 Non-Interventional Statistical Analysis Plan 01-Jun-2020

Table shell 22.1	Summary of COVID-19 variant by age groups
Table shell 22.2	Summary of COVID-19 variant by gender
Table shell 22.3	Summary of COVID-19 variant by BMI categories
Table shell 22.4	Summary of COVID-19 variant by smoking status
Table shell 22.5	Summary of COVID-19 variant by previous COVID-19 infection
Table shell 22.6	Summary of COVID-19 variant by COVID-19 vaccination history
Table shell 22.7	Summary of COVID-19 variant by underlying medical conditions
Table shell 23.1	Summary of duration to COVID-19 negative result(s) by age groups
Table shell 23.2	Summary of duration to COVID-19 negative result(s) by gender
Table shell 23.3	Summary of duration to COVID-19 negative result(s) by BMI categories
Table shell 23.4	Summary of duration to COVID-19 negative result(s) by smoking status
Table shell 23.5	Summary of duration to COVID-19 negative result(s) by previous COVID-19 infection
Table shell 23.6	Summary of duration to COVID-19 negative result(s) by COVID-19 vaccination history
Table shell 23.7	Summary of duration to COVID-19 negative result(s) by underlying medical conditions at index date
Table shell 23.8	Summary of duration to COVID-19 negative result(s) by medications used to treat COVID-19 in addition to nirmatrelvir, ritonavir
Table shell 23.9	Summary of duration to COVID-19 negative result(s) by days from COVID- 19 diagnosis to nirmatrelvir, ritonavir index date
Table shell 23.10	Summary of duration to COVID-19 negative result(s) by days from
	prescription to dispensing
Table shell 24	Summary of patients' hospitalization due to COVID-19 related reasons at
T 11 1 11 0 4 1	index date by covariates and univariate binary logistic models.
Table shell 24.1	Summary of patients' hospitalization due to COVID-19 related reasons at
	index date by covariates and the multivariable binary logistic model

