# Secondary analysis: To assess adult COVID-19 patients' HCRU within the 30-day period following nirmatrelvir, ritonavir prescription, including: Overall HCRU in inpatient and outpatient settings.

Healthcare Resource Use (HCRU) data will be summarized using descriptive statistics in terms of patient hospitalization, number of time patient hospitalization, cause of patient hospitalization, length of stay in the hospitalization, Intensive Care Unit (ICU) admission,

PFIZER CONFIDENTIAL CT24-WI-GL03-RF03 2.0 Non-Interventional Statistical Analysis Plan 01-Jun-2020 Page 19 of 42 number of Intensive Care Unit (ICU) admission, length of stay in Intensive Care Unit (ICU), supplemental oxygen use, type of oxygen, vasopressor use, patient intubation, outpatient visits, number of outpatient visits and reason of outpatient visits during the 30 days post index date and reported as shown in the *Table Shell 9*. Further stratification will be performed as described in section 3.2.

COVID-19 PCR and /antigen test result(s), Result(s) by PCR only, Result(s) by antigen test only, duration to COVID-19 negative result(s) by PCR and/antigen tests from the index date will be reported will be reported as shown in the *Table shell 21*.

COVID-19 variant by following stratifications will be reported as shown in the *Table shell 22.1 to 22.7: (if sample size permits)* 

- Age groups: *Table shell 22.1*
- Gender: *Table shell 22.2*
- BMI categories: *Table shell 22.3*
- Smoking status: *Table shell 22.4*
- Previous COVID-19 infection: *Table shell 22.5*
- COVID-19 vaccination history: Table shell 22.6
- Underlying medical conditions: Table shell 22.7

Duration to COVID-19 negative result(s) by following stratifications will be reported as shown in the *Table shell 23.1 to 23.10: (if sample size permits)* 

- Age groups: *Table shell 23.1*
- Gender: *Table shell 23.2*
- BMI categories: *Table shell 23.3*
- Smoking status: *Table shell 23.4*
- Previous COVID-19 infection: *Table shell 23.5*
- COVID-19 vaccination history: *Table shell 23.6*
- Underlying medical conditions: Table shell 23.7
- Medications used to treat COVID-19 in addition to nirmatrelvir, ritonavir: *Table shell 23.8*
- Days from COVID-19 diagnosis to nirmatrelvir, ritonavir index date: *Table shell* 23.9
- Days from prescription to dispensing (*if available*): *Table shell 23.10*

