COVID-19 infection	infection		during last 6 month will be
during the last 6 months			reported as count
Date of previous	Previous COVID-19	At index date	Date of previous COVID-19
COVID-19 infection	infection	At much date	infection during the last 6 will be
during the last 6	moonon		captured in (DD-MM-YYYY)
Duration between	Previous COVID-19	At index date	Duration between previous
previous COVID-19	infection		COVID-19 infection during last
infection during the			6 month from index date will be

Variables	Role	Time point(s)	Operational definition
last 6 months and index date			(Index date – Date of previous COVID-19 infection) /30.42
Medication used to treat previous COVID- 19 infection during the last 6	Previous COVID-19 infection	At index date	Medications used to treat previous COVID-19 infection during the last 6 will be reported as: Antiviral (Yes; No) If yes, Other, specify Antibiotic (Yes; No) If yes, Steroid (Yes; No) If yes, Steroid (Yes; No) If yes, Obexamethasone Prednisolone/Pr ednisone Prednisolone/Pr ednisone Hydrocortisone Other, specify Anti-thrombotic (Yes; No) If yes, Other, specify Anti-thrombotic (Yes; No) If yes, Other, specify Monoclonal antibody (Yes; No) If yes, Other, specify Monoclonal antibody (Yes; No) If yes, Other, specify Monoclonal antibody (Yes; No) If yes, Other, specify Hydroxychloroquine (Yes; No) If yes, Other, specify Hydroxychloroquine (Yes; No) If yes, Other, specify Hydroxychloroquine (Yes; No) If yes, Other, specify Immunosuppressant (Yes, No) If yes, Other, specify Intravenous immune globulin (Yes, No)

Variables	Role	Time point(s)	Operational definition
			
 
If yes,
 
Specify
 
Other medications (Yes; No)
 
If yes,
 
Specify
 

Date of Positive COVID-19 PCR/antigen test	COVID-19 infection data	At index date	Date of Positive COVID-19 PCR/antigen test will be captured in (DD-MM-YYYY)
Date of COVID-19 symptoms onset	COVID-19 infection data	At index date	Date of COVID-19 symptoms onset will be captured in (DD- MM-YYYY)
Duration between COVID-19 symptoms onset and index date (Days)	COVID-19 infection data	At index date	Duration of COVID-19 symptoms onset will be calculated as: (Index date – Date of COVID-19 symptoms onset)

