Frequency	Nirmatrelvir, ritonavir prescription data	At index date	Frequency of Nirmatrelvir/Ritonavir will be reported as: • Twice a day • Other • If Other, Specify (Open field)
Dispensed amount	Nirmatrelvir, ritonavir prescription data	At index date	Open field: Will be captured by Box, Blister and Tablets.
Dispensed date (if available)	Nirmatrelvir, ritonavir prescription data	At index date	Date of dispensed will be captured in (DD-MM-YYYY)
Days from COVID-19 diagnosis to nirmatrelvir, ritonavir prescription date	Nirmatrelvir, ritonavir prescription data	At index date	Days from COVID-19 diagnosis to nirmatrelvir, ritonavir index date will be calculated as: [Prescription date (Index date)- Date of COVID-19 diagnosis]
Days from COVID-19 diagnosis to nirmatrelvir, ritonavir prescription date (Categories)	Nirmatrelvir, ritonavir prescription data	At index date	Days from COVID-19 diagnosis to nirmatrelvir, ritonavir index date will be categorized as: • 0-2 days • 3-5 days • $\geq 6$ days
Days from prescription to dispensing	Nirmatrelvir, ritonavir prescription data	At index date	Days from prescription to dispensing will be calculated as: [Dispensed date- Prescription date (Index date)]
Days from prescription to dispensing (Categories)	Nirmatrelvir, ritonavir prescription data	At index date	Days from prescription to dispensing will be categorized as: • 0-2 days • 3-5 days

Variables	Role	Time point(s)	Operational definition
			• $\geq 6$ days
Days from COVID 19 symptoms onset to dispensing (if available)	Nirmatrelvir, ritonavir prescription data	At index date	Days from COVID 19 symptoms onset to dispensing will be calculated as: [Dispensed date- COVID-19 symptoms onset date]
Days from COVID 19 symptoms onset to dispensing (Categories)	Nirmatrelvir, ritonavir prescription data	At index date	Days from COVID 19 symptoms onset to dispensing will be categorized as: • 0-2 days • 3-5 days • ≥ 6 days
Days from COVID 19 symptoms onset to nirmatrelvir, ritonavir prescription (if available)	Nirmatrelvir, ritonavir prescription data	At index date	
 
Days from COVID 19 symptoms onset to nirmatrelvir, ritonavir prescription will be calculated as:
 
[Prescription date (Index date) COVID-19 symptoms onset date]
 

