or antigen test result(s)	data	day of post-	test result(s) will be reported as:
(If available)	uala	index period	Positive
			Negative
			• Indeterminate
COVID-19 PCR result	COVID-19 infection	During the 30	COVID-19 PCR test result will
(If available)	data	day of post-	be reported as:
	uata	index period	Positive
			Negative
			Indeterminate
COVID-19 Antigen	COVID-19 infection	During the 30	COVID-19 Antigen test result
test result	data	day of post-	will be reported as:
(If available)	data	index period	• Positive
			Negative
			Indeterminate
Date of COVID-19	COVID-19 infection	During the 30	Date of COVID-19 PCR/antigen
PCR/antigen test	data	day of post-	test will be captured in (DD-
	uata	index period	MM-YYYY)
Duration to Negative	COVID-19 infection	During the 30	Duration to negative COVID-19
COVID-19 test	data	day of post-	test after initiation of
(Months)	uata	index period	Nirmatrelvir, Ritonavir will be
			calculated as:
			(Date of Negative COVID-19
			result - Index date)/30.42

*COVID-19: Corona Virus Disease 2019 caused by SARS-CoV-2; PhD: Doctor of Philosophy; BMI: body mass index; PCR: polymerase chain reaction; ECMO: extracorporeal mechanical oxygenation; ER: emergency room; HCRU: Healthcare Resource Use; HFNC: high-flow nasal cannula; IMV: invasive mechanical ventilation; LOS: length of stay; NIMV: non-invasive mechanical ventilation*

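### Table shell 23.9 subtracts the diagnosis-to-prescription delay from the outcome it stratifies by that delay, so its strata are not comparable and may be misread as evidence on prescribing timing

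*SAP*

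**What the plan says.** SAP section 7.2 (secondary analysis) reports "duration to COVID-19 negative result(s) by PCR and/antigen tests from the index date". Annex 1 (Table 2) gives the same origin in its formula, the date of the negative test less the index date, converted to months: "result - Index date)/30.42". The index date is the prescription date (SAP Table 1, footnote a).

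The stratifier is defined in Annex 1 (Table 2) as "Prescription date (Index date)- Date of COVID-19 diagnosis", and section 4.2 cuts it at 0–2, 3–5 and ≥6 days. Section 7.2 lists "Days from COVID-19 diagnosis to nirmatrelvir, ritonavir index date" among the stratifications of the duration outcome, if sample size permits, and section 9 assigns it to shell 23.9, titled "Summary of duration to COVID-19 negative result(s) by days from COVID- 19 diagnosis to nirmatrelvir, ritonavir index date".

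Four other passages matter:
- Section 5.2 places duration to a negative test among the secondary endpoints, within the 30 days after index.
- Section 6 leaves patients with a missing continuous value out of the mean, median and quantiles. A patient with no recorded negative test therefore drops out and is not censored.
- Section 7.1 describes the study as descriptive, with no testing.
- Section 8 (limitations) does not mention the link between this outcome and this stratifier.

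**The concern.** The index date enters the outcome with a minus sign and the stratifier with a plus sign. A patient prescribed a week after diagnosis has spent that week before the outcome clock starts. A patient prescribed on the day of diagnosis has spent none. The two are compared as if their clocks began at the same point in the illness.

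Shell 23.9 would be read for what it says about prescribing delay, and a reader would see an unadjusted gradient with no warning that part of it may be arithmetic. The SAP's own background cites a study with better prognosis when treatment began within 5 days of diagnosis, so readers will come to the table with timing in mind.

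**Working it through.** **Inputs.** The definitions and bands are as above. The documents give no figure for time from diagnosis to negative or for prescribing delay, so there is no planned figure to reproduce, and every size below rests on an assumption. I take the diagnosis date to be the date of the positive test, which Annex 1 (Table 2) captures.

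**Algebra.** Let T = negative date − diagnosis date, D = index date − diagnosis date, and Y = the tabulated outcome. Then Y = T − D, so E[Y | D] = E[T | D] − D. If T does not depend on D and every patient is counted, Y falls by one day per day of delay.

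**Deterministic case.** Everyone turns negative 10 days after diagnosis and is prescribed on day 1, 4 or 7. Y = 10 − 1 = 9, 10 − 4 = 6 and 10 − 7 = 3 days. In the Annex's unit these are 9/30.42 = 0.296, 6/30.42 = 0.197 and 3/30.42 = 0.099 months.

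**Variable clearance, no timing effect.** T was simulated independently of D, keeping only negatives within 30 days after index. Delays were uniform over 0–9 days for the log-normal rows marked σ, and right-skewed over 0–10 days for the other rows. Entries are mean days from index to negative.

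| Assumed T (days) | 0–2 | 3–5 | ≥6 | First − last |
|---|---|---|---|---|
| Log-normal, median 8, σ 0.4 | 7.7 | 5.0 | 3.5 | 4.2 |
| Log-normal, median 10, σ 0.4 | 9.8 | 6.9 | 4.9 | 4.9 |
| Log-normal, median 14, σ 0.4 | 13.6 | 10.9 | 8.1 | 5.5 |
| Gamma, mean 8, SD 4 | 7.3 | 5.0 | 3.8 | 3.5 |
| Gamma, mean 10, SD 4 | 9.3 | 6.4 | 4.4 | 4.9 |
| Gamma, mean 14, SD 5 | 13.2 | 10.2 | 7.3 | 5.9 |
| Log-normal, mean 10, SD 6 | 9.0 | 6.6 | 5.6 | 3.4 |
| Log-normal, median 8, σ 0.8 | 8.5 | 7.4 | 7.4 | 1.1 |
| Log-normal, median 10, σ 0.8 | 10.0 | 8.6 | 8.3 | 1.7 |
| Log-normal, median 14, σ 0.8 | 12.3 | 10.6 | 10.0 | 2.3 |
| Exponential, mean 10 | 8.4 | 8.5 | 8.4 | 0 |
| Test dates set from prescription, mean 10 | 10.0 | 10.0 | 10.0 | 0 |

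The gap shrinks as the spread grows because only patients who turn negative after index are counted. In the late bands this removes the quick clearers and offsets part of the subtraction. For the gamma with mean 10 and SD 4, counting everyone would give 9.3, 6.1 and 2.5 days; the restriction raises the last figure to 4.4.

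**A real harm of delay.** Same gamma (mean 10, SD 4), with each day of delay prolonging T by b days. For b = 0.5 the table shows 9.6, 8.1 and 6.5 days, so late prescribing still looks better. The gradient vanishes only at b = 1 (10.0 in every band).

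**Plain from-diagnosis mean as a replacement.** For the same recorded patients, mean T in the first and last bands is:
- σ 0.4: 8.7 to 10.8 (median 8), 10.8 to 12.3 (median 10) and 14.6 to 15.6 (median 14), rises of 2.1, 1.5 and 1.0 days.
- σ 0.8: 9.5 to 14.7, 11.0 to 15.7 and 13.3 to 17.4, rises of 5.2, 4.7 and 4.1 days.

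The rise is larger still in the exponential case (9.1 to 15.7). Timing has no effect in any of these runs. The rise appears because a patient must not have turned negative before prescription to be counted.

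**The case against.** The strongest reply has three parts.

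1. **The gradient is not inevitable.** Testing follows routine care (SAP section 3.1). If test dates are set by the prescription, or clearance is memoryless, the table shows no gradient. Delay is also counted from diagnosis, not infection, so a patient diagnosed late and prescribed at once falls in the 0–2 band. This stands, and it limits the size. A reader might infer that late-prescribed patients will look faster purely by subtraction, and by a settled 4 to 5 days. The documents supply nothing that fixes such a figure, and real data would mix the artefact with testing practice, patient selection and any true effect.

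2. **The table is modest in status.** Time from prescription to negative is a legitimate descriptive quantity, the stratification is exploratory and conditional on sample size, and the SAP proposes no causal reading. This also stands: no test or primary result is affected. The full shells sit in a separate spreadsheet, so a footnote there cannot be ruled out. Descriptive status does not make the bands comparable, however, and the SAP text carries no caution.

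3. **The obvious remedy is unsound.** A reader might infer that measuring from diagnosis settles the matter. The figures above show that it does not: under wide spread, the opposite gradient of 4 to 5 days exceeds the 1 to 2 days removed.

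A reader might also infer that the table would contradict the study cited in the background. That study concerns prognosis in immunocompromised inpatients, which is a different quantity.

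**Conclusion.** The concern holds in limited form. By the SAP's own definitions, shell 23.9 tabulates T − D within bands of D, so its strata are not comparable, and nothing in the SAP text corrects or discloses this. With no timing effect on clearance, the table would tend to show shorter times with later prescribing.

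The size depends on assumptions that the documents do not supply: roughly 3.5 to 6 days between first and last bands when clearance times vary little to moderately, 1 to 2 days when they vary widely, and none in the two boundary cases. The artefact can mask or reverse a modest real harm of delay. The consequence is possible misinterpretation of one exploratory table. The change is worth making because it is cheap.

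**What to change.** In SAP section 7.2 and Annex 1 (Table 2), add a derived variable: days from positive test to negative test, from dates already captured. In shell 23.9:
- Show it beside the from-index duration, in days, estimated with delayed entry at the index date and censoring 30 days after index for patients with no negative test.
- For the ≥6-day band, report it only conditional on being still positive at entry, since nobody in that band is under observation before day 6.
- Footnote that the from-index figure falls with delay by construction.
- Footnote that a simple from-diagnosis mean runs long in the late bands (about 1 to 5 days under the log-normal assumptions above), because patients must not have turned negative before prescription.

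If this is not done, drop shell 23.9 or footnote that its strata must not be compared as evidence on prescribing timing. Do not simply replace the outcome with the from-diagnosis mean.

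The cost is one derived variable, a little more analysis and some SAP wording, with no new data. Some residual selection remains in the ≥6-day band.
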